8.2 Measurement of Treatment Compliance

Dosing compliance for a specified period is defined as the total number of capsules of study treatment taken by a patient during the treatment period divided by the number of capsules of study treatment that were expected to be taken during the treatment period multiplied by 100.

The total number of capsules taken during the treatment period will be calculated from the study treatment record. Descriptive statistics for study treatment dosing compliance together with compliance category will be summarized by treatment group for the Safety Population.

8.3 Prior and Concomitant Medication

The latest version of the *World Health Organization Drug Global* (WHODG) will be used to code prior, prior concomitant, and concomitant medications. *Prior medication* is defined as any medication started and stopped before the date of the first dose of double-blind study treatment. A *prior concomitant medication* is any medication that started before the date of the first dose of double-blind study treatment and stopped or is ongoing after the date of the first dose of study treatment. *Concomitant medication* is defined as any medication taken on or after the date of the first dose of double-blind study treatment. Both prior and concomitant medications, including prior concomitant medication use, will be summarized as the number and proportion of patients in each treatment group who received each medication within each therapeutic class (ie, Anatomical Therapeutic Chemical code, Levels 2, 3 and 4) and preferred term for the Safety Population. Multiple medications used by a patient will only be counted once.

Any concomitant medication started after the date of the last dose of double-blind study treatment will not be included in the summary but will be included in the patient data listings.

Confidential Page 19 of 72

9. EFFICACY ANALYSES

The primary efficacy analyses and will be based on the mITT Populations, respectively; other efficacy analyses will be based on the ITT Population, unless stated otherwise. The baseline for each specific efficacy endpoint is defined as the last measurement prior to the first dose of randomized treatment. All statistical hypothesis tests will be performed at the 2-sided 5% significance level for main effects. All confidence intervals (CIs) will be 2-sided 95% CIs, unless stated otherwise.

All investigative sites with fewer than 2 mITT patients per treatment group will be pooled as follows: The largest site with fewer than 2 mITT patients per treatment group will be pooled with the smallest site with fewer than 2 mITT patients per treatment group within the same country. If this results in a pooled site still having fewer than 2 mITT patients per treatment group, this site will be pooled together with the next smallest investigative site within the same country. If a pooled site having all patients enrolled from one country still has less than 2 patients in either treatment group, then this pooled site would be included in the site pooling in the country with the second smallest enrollment. Sites with the same number of mITT patients will be ordered in ascending order of their numerical site identification number. This will serve as a tie-breaker rule in case multiple sites have the same number of mITT patients. Should the primary efficacy analysis model present convergence issues, after testing the sequence of correlation structures, then the site effect will be reconsidered and may be dropped from the model. These pooled investigative sites, as determined based on the primary efficacy response variable, will be used for all analyses that has investigative site as a fixed effect in the model. The actual investigative site numbers will be included in the listings.

	İ
	I
_	

Confidential Page 20 of 72

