The primary efficacy endpoint will be change from Baseline to Day 43 in MADRS total score. Based on the primary hypothetical estimand strategy which assumes patients are on study treatment up to the primary time point (Day 43), efficacy data collected after discontinuation of study treatment (ie, efficacy assessment performed more than 3 days after last dose of study treatment) and/or after starting new ADT will be set to missing and will not be included in the primary analysis. Instead, these missing data will be assumed as missing at random. The primary analysis to estimate and compare the treatment effects of lumateperone vs placebo as defined by the primary estimand will be performed using a mixed-effects model for repeated measures (MMRM) with change from baseline at each study visit as the response variable, and treatment group, study site (or pooled site) and study visit as factors, baseline MADRS total score as covariate, and interaction terms for baseline MADRS total score-by-study visit and treatment groupby-study visit. An unstructured covariance matrix will be used to model the covariance of within-patient scores. The Kenward-Roger approximation will be used to estimate the denominator degrees of freedom. Treatment difference will be estimated via contrast based on treatment group and treatment group-by-study visit factors.

The key secondary efficacy parameter will be the change from baseline to Day 43 in CGI-S score. The key secondary efficacy parameter will be analyzed using a similar MMRM as used for the primary analysis with the baseline CGI-S score for the covariate.

A fixed sequence testing procedure will be used to control the overall Type I error of 0.05 with the primary endpoint tested first at the 2-sided 0.05 level, and if significant, the key secondary endpoint will be tested at the 2-sided 0.05 level.

Primary efficacy analyses will be based on the modified Intent-to-Treat (mITT) Population, defined as all randomized patients who received at least 1 dose of study treatment, have an evaluable baseline assessment of MADRS total score, and have at least one evaluable post-baseline, on-treatment assessment of the MADRS total score (on-treatment MADRS assessments are those performed no later than 3 days after the last dose of study treatment).

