Key secondary efficacy analyses will also be based on the mITT Population. An estimation and comparison of the treatment effects of lumateperone vs placebo for the key secondary endpoint are based on the hypothetical estimand (similar to that defined for the primary analysis, using assessed CGI-S score up to 3 days after last study dose and not including those assessed after new ADT).

All safety parameters will be summarized descriptively. Safety analyses will be based on the Safety Population defined as all randomized patients who received at least one dose of investigational product.

Individual plasma concentrations will be listed and summarized by visit. Plasma concentrations will be analyzed using a population PK approach. The results from the population PK analyses will be presented in a separate report.

Approximately 470 patients will be randomly assigned to 1 of the 2 treatment groups (lumateperone 42 mg or matching placebo). Assuming a common drop-out rate of 20% and a common correlation of 0.7 between the repeated measures, the sample size of 235 patients per treatment group will provide approximately 90% statistical power for the effect size of 0.33 (treatment difference of 3.3 and common pooled standard deviation of 10) for the primary efficacy endpoint.

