9.4.5 Efficacy Analyses

The primary efficacy analyses and the sensitivity analysis will be based on the mITT and ITT Populations; other efficacy analyses will be based on the ITT Population, unless stated otherwise. The baseline for each specific efficacy endpoint is defined as the last measurement prior to the first dose of randomized treatment. All statistical hypothesis tests will be performed at the 2-sided 5% significance level for main effects. All confidence intervals (CIs) will be 2-sided 95% CIs, unless stated otherwise.

All investigative sites with fewer than 2 mITT patients per treatment group will be pooled as follows: The largest site with fewer than 2 mITT patients per treatment group will be pooled with the smallest site with fewer than 2 mITT patients per treatment group within the same country or geographic region. If this results in a pooled site still having fewer than 2 mITT patients per treatment group, this site will be pooled together with the next smallest investigative site within the same country or geographic region, if one exists; otherwise, no further pooling is needed. Sites with the same number of mITT patients will be ordered in ascending order of their numerical site identification number. This will serve as a tie-breaker rule in case multiple sites have the same number of mITT patients. Should the primary efficacy analysis model present convergence issues, after testing the sequence of correlation structures, then the site effect will be reconsidered and may be dropped from the model. These pooled investigative sites, as determined based on the primary efficacy response variable, will be used for any analysis that has investigative site as a fixed effect in the model. The actual investigative site numbers will be included in the listings. For analyses that are based on the ITT Population and include site as a factor, additional pooling will be performed starting from the mITT pooled sites. Sites with patients who are in ITT Population but not the mITT Population will be pooled, using the same algorithm as outlined above.

[figure not shown]

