3.1 Efficacy Objectives and Estimands

3.1.1 Primary Objective

The primary efficacy objective of this study is to evaluate the efficacy of lumateperone 42 mg administered once daily compared to placebo as adjunctive treatment to ADT in patients with MDD who have an inadequate response to ongoing ADT as measured by change from baseline to Day 43 in the Montgomery-Åsberg Depression Rating Scale (MADRS) total score.

The hypothetical estimand strategy is considered to address the primary objective and it is described as follows:

- Target Population: Patients with MDD who have an inadequate response to ongoing ADT
- Treatment: Lumateperone 42 mg vs placebo as adjunctive therapy to existing ADT
- Variable (Endpoint): Change from baseline to Day 43 in the MADRS total score
- Intercurrent events (ICE) and corresponding strategies (see Table 3-1)
- Summary measure: Difference in treatment means between lumateperone 42 mg and placebo.

Confidential Page 11 of 72

The primary estimand, based on the hypothetical strategy defined by the above 5 attributes, quantifies the efficacy of lumateperone vs placebo with regard to the premature discontinuation of study treatment as adjunctive to existing ADT and in the absence of newly introduced ADT in patients after randomization. This strategy accounts for use of the primary efficacy data based on MADRS assessments while patients who prematurely discontinue are assumed to be on study treatment for the entire 6 weeks treatment period and eliminating potential effect of newly initiated ADT.

Confidential Page 12 of 72

Confidential Page 13 of 72

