The MMRM is being considered as the statistical model for the estimation of the primary and key secondary estimands to compare the treatment effect between the lumateperone 42 mg group and the placebo group in combination with the fixed-sequence testing procedure (first test for the primary efficacy endpoint and, if significant, then test for the key secondary efficacy endpoint) for the analyses of the primary and key secondary efficacy endpoints for the proposed 6-week double-blind, placebo-controlled studies in patients with MDD with mixed features.

_		

Confidential Page 22 of 72

Confidential Page 23 of 72

Confidential Page 24 of 72

	Т.
•	
-	

Confidential Page 25 of 72

[figure not shown]

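### Do the ITT default for the key secondary analysis and the mixed-features wording in SAP Section 9 put the alpha-controlled tests on the wrong population?

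*SAP*

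**What the plan says.** **Analysis set.** The protocol synopsis puts both alpha-controlled tests on mITT: "Primary efficacy analyses will be based on the modified Intent-to-Treat (mITT) Population", and "Key secondary efficacy analyses will also be based on the mITT Population". Protocol 9.4.5 reads differently: "The primary efficacy analyses and the sensitivity analysis will be based on the mITT and ITT Populations; other efficacy analyses will be based on the". That sentence ends by making ITT the default for those other analyses, and 9.4.5.2.1 names no set for CGI-S. The opening of SAP Section 9 reads "The primary efficacy analyses and will be based on the mITT Populations, respectively", followed by "other efficacy analyses will be based on the ITT Population, unless stated otherwise". The readable text of SAP 9.2.1 gives the estimand strategy, the missing-data rule and the model for CGI-S, but no analysis set. It refers to a Table 9-3 that the public version does not show.

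**Site pooling.** Protocol 9.4.5 says: "For analyses that are based on the ITT Population and include site as a factor, additional pooling will be performed". The readable SAP Section 9 instead applies a single set of pooled sites, built from mITT counts, to every analysis with site as a fixed effect.

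**Target population.** SAP 3.1.1 defines it as "patients with MDD who have an inadequate response to ongoing ADT", and SAP 3.1.2 carries it over to CGI-S. SAP 9.1.1 twice describes the population as MDD with mixed features, once in the form "double-blind, placebo-controlled studies in patients with MDD with mixed features".

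**The concern.** CGI-S is the second step of the fixed sequence and is tested at the two-sided 0.05 level once MADRS succeeds. If one document puts it on mITT and another on ITT, two p-values could each claim to be the pre-specified one. The protocol's extra pooling for ITT analyses suggests that the site factor could differ as well.

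The mixed-features wording looks worse. Target population is one of the five attributes of the estimand. Here the section that specifies the primary and key secondary analyses names a group that no eligibility criterion selects. Taken literally, the test would support a claim about patients the trial did not set out to recruit.

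**Working it through.** **1. The plan's own figure.** Protocol 9.2 gives a difference of 3.3, SD 10, 235 per arm, 20% dropout and about 90% power.
- Completers per arm: 235 × 0.8 = 188.
- Standard error of the difference, in SD units: √(2/188) = 0.103.
- Power: Φ(0.33/0.103 − 1.96) = 89.2%, which reproduces the stated figure.
- Closed-form MMRM information with six visits and correlation 0.7 gives 92.2% to 92.6%. Equal correlation across visits and linear dropout are assumptions.

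These figures depend on N, alpha and dropout, not on which set is named for CGI-S.

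**2. Who is in ITT but not in mITT.** ITT requires a dose and a baseline MADRS. mITT adds at least one post-baseline MADRS no later than 3 days after the last dose. The difference is therefore patients with no on-treatment post-baseline MADRS.

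**3. What those patients add to the CGI-S model.** SAP 9.2.1 sets to missing any CGI-S taken more than 3 days after the last dose or after new ADT, and then fits an MMRM to the observed changes. A patient with no remaining CGI-S has no rows and leaves the likelihood unchanged. The documents give no rate for such patients, so a range is assumed, using the primary endpoint's inputs:

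| No post-baseline value | ITT N | mITT N | Power, ITT | Power, mITT |
|---|---|---|---|---|
| 1% | 470 | 470 × 0.99 ≈ 465 | 92.5% | 92.5% |
| 2% | 470 | 470 × 0.98 ≈ 461 | 92.4% | 92.4% |
| 5% | 470 | 470 × 0.95 ≈ 447 | 91.9% | 91.9% |
| 10% | 470 | 470 × 0.90 = 423 | 91.2% | 91.2% |

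A simplified repeated-measures model (random intercept, no site or baseline term) fitted to one simulated dataset gave −0.2768 with SE 0.0959, both for all 470 patients and for the 452 with a post-baseline value. This is expected, because the other 18 supply no data.

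**4. The one route to a difference.** It needs a patient with an on-treatment CGI-S and no on-treatment MADRS at any post-baseline visit. SAP Table 15-1 gives the two scales the same weekly windows, and the 3-day rule is the same, so this happens only when one scale is rated and the other missed throughout. To size it, take one such patient with a Week 1 CGI-S only, lying 2 SD from the arm mean (an assumption), and carry the plan's 0.7 correlation over to CGI-S (also an assumption):
- Shift in the Day 43 arm mean: about 0.7 × 2 / 235 = 0.006 SD.
- Relative to the standard error: 0.006 / 0.103 ≈ 0.06.
- A result at z = 1.96 would move to 1.90 (p = 0.057) or 2.02 (p = 0.043).

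Only a result already on the boundary would change sides.

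**5. Site factor.** The readable SAP uses one mITT-based pooling for all analyses with a site effect, and protocol 9.1 allows the SAP to change analysis methods. Under the protocol's version, the extra step starts from the mITT pools. On the natural reading it attaches sites that have only non-mITT patients. Those sites bring no CGI-S rows except through the patient in step 4.

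**6. Mixed features.** Inclusion criterion 3 requires DSM-5 MDD and accepts psychotic features. Criterion 4 requires inadequate response to ADT. No inclusion or exclusion criterion mentions mixed features. The two sentences in SAP 9.1.1 explain why the strategy and the MMRM are being considered; they define no subset, covariate or filter.

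**The case for a change.** The strongest case for acting is that a test carrying alpha should have its analysis set named once, where the test is specified, and that a wrong target population in operative text should not stand when the correction costs a few words. The protocol's sentence parallel to the gap in the SAP concerns the sensitivity analysis, so the missing SAP words probably did too and did not assign CGI-S to mITT. Table 9-3 is cited for intercurrent events, not for an analysis set.

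Much of this stands. The synopsis disagrees with protocol 9.4.5 and with the readable SAP, and the mixed-features phrase is wrong for this trial. Several points do not carry further:
- The primary is on mITT in both the SAP and the synopsis, so at most one of the two tests is affected.
- The conflict begins inside the protocol; the SAP default follows the protocol body.
- The incomplete SAP sentence is consistent with withheld text and cannot be counted as an error. The ITT default also yields to any statement elsewhere, so the public version cannot show that the SAP assigns ITT.
- What is left is tidiness of wording, since either set gives in effect the same CGI-S result.

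**Conclusion.** No change to the plan follows. The analysis-set discrepancy is a drafting inconsistency with no practical consequence. Whichever set the analyst uses, the same CGI-S rows enter the same model, apart from the rare patient rated on CGI-S but never on MADRS while on treatment; one such patient is worth about 0.06 of a standard error under the assumptions shown. Sample size, power and type I error are unaffected. The mixed-features phrase is a clerical slip in explanatory sentences, and SAP 3.1.1, SAP 3.1.2 and the eligibility criteria leave no doubt about who is studied.

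This rests on three things: the two scales being rated at the same visits, as Table 15-1 implies; the key secondary being analysed by MMRM on observed on-treatment data, as SAP 9.2.1 states; and the single pooling rule in the readable SAP holding. If many patients had CGI-S without MADRS, the two sets could diverge, but nothing in the documents points to that.

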9.1 Primary Efficacy Endpoint

The primary efficacy endpoint is the change from baseline to Day 43 in the MADRS total score.

[figure not shown]
9.1.1 Primary Efficacy Analysis

The primary efficacy analysis will be assessed for the hypothetical estimand and the data to be included in this primary analysis will be decided by the intercurrent events as described in Table 3-1.

Based on the primary hypothetical estimand strategy which assumes patients are on study treatment up to the primary time point, efficacy data collected after discontinuing study treatment (ie, performed more than 3 days after last dose of study treatment) or after starting new ADT will be set to missing and will not be included in the primary analysis. Instead, these missing data are assumed as missing at random (MAR).

The hypothetical estimand strategy is being considered to address the primary and key secondary efficacy objectives for the proposed 6-week, double-blind, placebo-controlled study in patients
with MDD with mixed features.

The primary analysis to estimate and compare the treatment effects of lumateperone vs placebo as defined by the primary estimand will be performed using a mixed-effects model for repeated measures (MMRM) method. The model will include the change from baseline in MADRS total score at each study visit as the response variable, and treatment group, study visit, site (or pooled site) as factors and the baseline MADRS total score as covariate, and interaction terms for baseline MADRS total score-by-study visit and treatment group-by-study visit. An unstructured covariance matrix will be used to estimate the correlation among repeated measurements within patient. The Kenward-Roger approximation (Kenward and Roger, 1997) will be used to estimate the denominator degrees of freedom. The mean treatment difference for lumateperone vs placebo will be estimated via contrast based on treatment group and treatment group-by-study visit factors and will be reported along with the corresponding 95% CI and the p-value for superiority testing.

Confidential Page 21 of 72

The MMRM is being considered as the statistical model for the estimation of the primary and key secondary estimands to compare the treatment effect between the lumateperone 42 mg group and the placebo group in combination with the fixed-sequence testing procedure (first test for the primary efficacy endpoint and, if significant, then test for the key secondary efficacy endpoint) for the analyses of the primary and key secondary efficacy endpoints for the proposed 6-week double-blind, placebo-controlled studies in patients with MDD with mixed features.

_		

Confidential Page 22 of 72

Confidential Page 23 of 72

Confidential Page 24 of 72

	Т.
•	
-	

Confidential Page 25 of 72

[figure not shown]

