- 3. Meets DSM-5 criteria for MDD (MDD with psychotic features will be acceptable) as confirmed by the Investigator or Sponsor-approved rater using the MINI and meets all of the following criteria:
 - a. The start of the current major depressive episode (MDE) is at least 8 weeks but not more than 18 months prior to Screening (Visit 1);
 - b. Has at least moderate severity of illness based on rateradministered MADRS total score ≥ 24 at Screening (Visit 1) and at Baseline (Visit 2);
 - c. Has at least moderate severity of illness based on CGI-S score ≥ 4 at Screening (Visit 1) and at Baseline (Visit 2);
 - d. Has a Quick Inventory of Depressive Symptomatology-Self Report-16 item (QIDS-SR-16) score ≥ 14 at Screening (Visit 1) and at Baseline (Visit 2);
 - e. Has sufficient history and medical record confirmation verifying the ADT and the current MDE is causing clinically significant distress or impairment in social, occupational, or other important areas of functioning.
- 4. Currently having an inadequate response to ADT (less than 50% improvement) as confirmed by the Investigator using the Antidepressant Treatment Response Questionnaire (ATRQ) and taking at least the minimum effective dose (per package insert) of one of the following antidepressants as monotherapy treatment for at least 6 weeks duration:
 - a. citalopram/escitalopram
 - b. fluoxetine
 - c. paroxetine
 - d. sertraline
 - e. duloxetine
 - f. levomilnacipran/milnacipran (if locally approved for MDD)
 - g. venlafaxine/desvenlafaxine
 - h. bupropion
 - i. vilazodone
 - i. vortioxetine

All Inclusion Criteria are presented in Section 6.3.1.

Main Exclusion Criteria

Patients who meet any of the following exclusion criteria will not be able to participate in the study:

- 1. Within the patient's lifetime, has a confirmed DSM-5 psychiatric diagnosis other than MDD, including:
 - a. Schizophrenia, Schizoaffective Disorder, Schizophreniform Disorder or other psychotic disorder;
 - b. Bipolar Disorder;
- 2. Within 6 months of Screening, has a confirmed DSM-5 psychiatric diagnosis other than MDD including:
 - a. Anxiety disorders such as Panic Disorder or Generalized Anxiety Disorder; Obsessive-compulsive Disorder; Posttraumatic Stress Disorder as primary diagnoses. Note: Anxiety symptoms may be allowed if secondary to MDD, provided these symptoms do not require concurrent treatment;
 - b. Eating disorder;
 - c. Substance use disorders (excluding nicotine);

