8.1.5 Patient Placebo Questionnaire and Training

A brief training module will be provided describing placebo response at Baseline (Visit 2) prior to randomization. A placebo response questionnaire will be administered at Baseline (Visit 2) prior to randomization to assess the patient's perception of likelihood their symptoms will improve as well as their perception at the end of the study whether they received placebo or active study treatment.

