9.2 Determination of Sample Size

The effect size (treatment group difference relative to pooled standard deviation) of 0.33 for lumateperone 42 mg is based on a treatment difference of 3.3 units with a common pooled SD of 10 for the primary efficacy endpoint, change from baseline to Day 43 in MADRS total score. A sample size of 470 patients (235 per treatment group) will be needed to provide approximately 90% power for primary analysis (lumateperone 42 mg vs placebo) based on an MMRM model using simulation method (Lu, 2012). The simulation assumed a correlation of 0.7 between the repeated measures and a common dropout rate of 20% based on historical data.

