9.2.1 Key Secondary Analysis

The key secondary efficacy endpoint will be tested using the same hypothetical estimand strategy as for the primary efficacy endpoint.

The data to be included in the key secondary efficacy analysis will be decided by the intercurrent events as described in Table 9-3.

Based on the key secondary hypothetical estimand strategy which assumes patients are on treatment up to the Day 43 assessment, efficacy data collected after discontinuing study treatment (ie, performed more than 3 days after last dose of study treatment) or after starting new ADT will be set to missing and will not be included in the key secondary analysis. Instead, the missing data are assumed as missing at random.

The key secondary efficacy endpoint will be analyzed using an MMRM method similar to the one specified for the primary efficacy endpoint while substituting MADRS total-score-related variables in the model with the corresponding CGI-S-related ones, such as baseline score and visit-by-baseline score interaction.

Confidential Page 26 of 72

_	

Confidential Page 27 of 72

Confidential Page 28 of 72

10. SAFETY ANALYSES

Safety analyses will be performed using the Safety Population. The safety parameters will include AEs, clinical laboratory, vital signs, ECG, and EPS (AIMS, BARS, and SAS) and C-SSRS scales. The baseline for each safety endpoint is defined as the last measurement prior to the first dose of randomized treatment.

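### Both confirmatory MMRMs are valid but forgo some precision: baseline QIDS-SR-16 is not in the primary model, and baseline MADRS is swapped out of the CGI-S model

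*SAP*

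**What the plan says.** SAP 9.1.1 fits an MMRM to change from baseline in MADRS total score. Its terms are treatment, visit, "site (or pooled site) as factors and the baseline MADRS total score as covariate", plus baseline-by-visit and treatment-by-visit interactions. The protocol synopsis gives the same model.

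SAP 9.2.1 forms the CGI-S model by "substituting MADRS total-score-related variables in the model with the corresponding CGI-S-related ones". The synopsis likewise names baseline CGI-S as the covariate. QIDS-SR-16 appears in neither model, and baseline MADRS is absent from the second. The visible text gives no reason. Parts of SAP section 9 are redacted, but both confirmatory model statements can be read.

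The unused scores are collected anyway:

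- **QIDS-SR-16.** Inclusion criterion 3d in the synopsis requires "QIDS-SR-16) score ≥ 14 at Screening (Visit 1) and at Baseline (Visit 2"). Exclusion criterion 4 compares the Screening and Baseline scores, so both must be recorded.
- **MADRS.** Entry requires at least 24 at both visits. SAP 4.3 and 4.4 make a baseline MADRS score a condition of belonging to the ITT and mITT Populations.
- **CGI-S.** Entry requires at least 4 on the seven-point scale of Protocol 8.2.2.

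**The concern.** In a randomized comparison analysed with a linear model, a prespecified prognostic baseline covariate removes explainable variance from the residual and leaves the target of estimation unchanged. Leaving out a useful one gives a wider confidence interval and less power.

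The point is clearest for CGI-S. At baseline that score can take only four values, 4 to 7, while MADRS can run from 24 to 60. The substitution therefore drops the finer severity measure, which is complete by definition in the population analysed, and keeps only the coarser one.

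For the primary endpoint, QIDS-SR-16 is a patient-rated measure and could carry some information beyond the rater's MADRS.

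Both tests are alpha-controlled in a fixed sequence, with the "primary endpoint tested first at the 2-sided 0.05 level". Precision lost on MADRS therefore also affects whether CGI-S is tested at all.

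**Working it through.** **Inputs from Protocol 9.2.** The plan states: "A sample size of 470 patients (235 per treatment group) will be needed to provide approximately 90% power for primary analysis". It assumes a "treatment difference of 3.3 units with a common pooled SD of 10". It adds: "The simulation assumed a correlation of 0.7 between the repeated measures and a common dropout rate of 20% based on historical data". The test is two-sided at 0.05.

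**Step 1: reproduce the stated power.** Completers per arm = 235 × 0.8 = 188. SE of the difference = 10 × √(2/188) = 1.031. Power = Φ(3.3/1.031 − 1.96) = Φ(1.24) = 89.2%, against the stated 90% or so. An asymptotic MMRM variance with six post-baseline visits and monotone 20% dropout gives 89.4% to 90.5% under AR(1) correlation of 0.7, and 92.1% to 92.6% under compound symmetry of 0.7. The stated figure stands.

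**Step 2: effect of an added covariate on the primary test.** Let r be the partial correlation of baseline QIDS-SR-16 with Day 43 change, given the terms already in the model. The documents do not give r, so 0.1 to 0.3 is an assumption. SD 10 is taken as the residual SD under the planned model, and the residual variance is assumed to shrink by the factor 1 − r² at every visit.

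- Noncentrality for 90% power: 1.960 + 1.2816 = 3.24
- Power after adjustment: Φ(3.24/√(1 − r²) − 1.96)
- Equivalent patients: 470 × r²
- SE multiplier: √(1 − r²)

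| r | Variance removed | SE multiplier | Power | Equivalent patients |
|---|---|---|---|---|
| 0 | 0% | 1.000 | 90.0% | 0 |
| 0.1 | 1% | 0.995 | 90.3% | 4.7, about 5 |
| 0.2 | 4% | 0.980 | 91.1% | 18.8, about 19 |
| 0.3 | 9% | 0.954 | 92.5% | 42.3, about 42 |

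**Step 3: cross-check from the reproduced 89.2%.** With 188 completers per arm, removing 1%, 5% or 10% of the residual variance gives 89.5%, 90.7% or 92.1%, a gain of 0.3, 1.5 or 2.9 points. If the true difference were 3.0, power would go from 82.9% to 84.7% (5% removed) or 86.6% (10% removed).

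**Step 4: CGI-S.** The documents state no CGI-S effect, SD or correlation, so the gain from keeping baseline MADRS cannot be computed.

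**Step 5: cost in the model.** One covariate with its visit interaction over six post-baseline visits adds 1 + 5 = 6 fixed-effect parameters and no covariance parameters.

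**The case against.** The strongest reply is that this is an optional refinement. The plan already adjusts for the endpoint's own baseline, by visit, and for site, and its power statement checks out. The benefit rests wholly on an assumed correlation. QIDS-SR-16 and MADRS both measure depressive severity. Both are truncated at entry (at 14 and 24), and a fall of 25% or more on either before Baseline excludes the patient. Little independent information may remain once baseline MADRS is in the model. This stands: the low end of the table is credible, and a gain of 0.3 points would not be noticed.

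Two practical objections also stand, and they shape the fix:

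- The mITT definition guarantees a baseline MADRS but not a baseline QIDS-SR-16. A protocol deviation that left it blank would drop that patient from a standard MMRM.
- SAP section 9 defines baseline for efficacy endpoints. QIDS-SR-16 is described among the screening-period assessments (Protocol 8.1.6) and is not among the baseline efficacy parameters listed in SAP section 7, so it needs its own baseline definition.

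A reader might go further in three ways that the documents do not support:

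- **That both models ignore baseline MADRS, or adjust for nothing but own baseline.** Baseline MADRS is the covariate in the primary model, and site or pooled site is in both.
- **That the analysis is invalid or the trial undersized.** Neither follows from an omitted precision covariate.
- **That the pre-randomization expectancy questionnaire should be added too.** Protocol 8.1.5 says only that it will "assess the patient's perception of likelihood their symptoms will improve", along with the patient's perception of which treatment was received. No items, scale or total score are given, and it is not an eligibility requirement, so neither its form as a covariate nor its completeness can be assumed.

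**Conclusion.** The point holds as a modest missed gain in precision. The SAP's confirmatory models are correct as written. They leave unused one severity baseline that every eligible patient should have (QIDS-SR-16, primary model) and one that every analysed patient has by definition (MADRS, CGI-S model).

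For the primary test the gain is about 0.3 to 2.5 points of power, or about 5 to 42 of 470 patients, over assumed partial correlations of 0.1 to 0.3. The range is not drawn from the documents, and its lower end is plausible.

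For CGI-S the argument from completeness and scale is stronger, but no figure can be attached. The case for acting is that the cost is close to nil even if the gain proves small.

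**What to change.** Make these changes before unblinding:

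1. **SAP 9.2.1:** keep baseline MADRS total score and its visit interaction alongside baseline CGI-S and its visit interaction.
2. **SAP 9.1.1:** add baseline QIDS-SR-16 total score and its visit interaction, with baseline defined as the last value before first dose.
3. **Missing QIDS-SR-16:** state a simple rule, such as imputing the overall mean across both arms, so that no mITT patient is dropped for lack of this covariate.
4. **Documentation:** record the change from the model in the protocol synopsis. Protocol 9.1 allows this through the SAP without a protocol amendment, but requires the departure to be documented and justified in the clinical study report.

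The cost is SAP wording, six extra fixed-effect parameters in each model and a sentence of justification in the report. No new data are needed.
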